6.3.2 Treatment Phase

During the treatment phase the following assessments are to be performed (see Schedule of Study Events in Table 4 for timing of assessments in each cycle).

Physical examination and vital signs	
 • Body weight • Blood pressure, pulse, temperature • Physical examination (symptom directed)
Urine analysis (every other cycle)	Urine bilirubin, glucose, hemoglobin, ketones, pH, protein
Hematology	Hemoglobin, hematocrit, mean corpuscular volume, mean corpuscular hemoglobin, mean corpuscular hemoglobin concentration, white blood cell (WBC) count, WBC differential, red blood cell count, lymphocytes, monocytes, neutrophils, band neutrophils, eosinophils, basophils, platelets. WBC differential may be automated or manual as per institutional standards.
Complete clinical chemistry	Sodium, potassium, chloride, bicarbonate, BUN, creatinine, glucose, calcium, phosphate, magnesium, ALT, AST, alkaline phosphatase, total bilirubin, total protein, albumin
TSH	If TSH is abnormal, free T3 and free T4 will also be measured. Repeat TSH every 3 rd cycle
Pregnancy test (if applicable)	A urine pregnancy test will be performed on cycle 1 day 1 and every 3 rd cycle or if pregnancy is suspected in women of child-bearing potential: pre-

PROTOCOL NUMBER: OSU-19132

	menopausal women and women who are post-menopausal for < 2 years.
Adverse events and concomitant medication	Assessed on an ongoing basis

6.3.3 Tumor Imaging and Assessment of Disease

Tumor imaging is strongly preferred to be acquired by computed tomography (CT). For the abdomen and pelvis, contrast-enhanced magnetic resonance imaging (MRI) may be used when CT with iodinated contrast is contraindicated, or when local practice mandates it. MRI is the strongly preferred modality for imaging the brain. The same imaging technique regarding modality, ideally the same scanner, and the use of contrast should be used in a participant throughout the study to optimize the reproducibility of the assessment of existing and new tumor burden and improve the accuracy of the assessment of response or progression based on imaging.

Expedited confirmation of measurable disease based on RECIST 1.1 at Screening should be used to determine participant eligibility. Confirmation that the participant's imaging shows at least 1 lesion that is appropriate for selection as a target lesion per RECIST 1.1 is highly recommended prior to participant enrollment.

6.3.4 Initial Tumor Imaging

Initial tumor imaging at Screening must be performed within 28 days prior to the start of study treatment. The site study team must review screening images to confirm the participant has measurable disease per RECIST 1.1 prior to first dose of study treatment.

Brain imaging, if performed to document the stability of existing metastases, should be by MRI if possible. If MRI is medically contraindicated, CT with contrast is an acceptable alternative.

6.3.5 Tumor Imaging on Study

The first on-study imaging assessment should be performed at 6 weeks (42 days \pm 7 days) from the date of allocation. Subsequent tumor imaging should be performed every 6 weeks (42 days \pm 7 days) or more frequently if clinically indicated. After 6 months, participants who remain on treatment will have imaging performed every 12 weeks (84 days \pm 7 days). Imaging timing should follow calendar days and should not be adjusted for delays in cycle starts. Imaging should continue to be performed until disease progression is identified by the Investigator.

Objective response should be confirmed by a repeat imaging assessment. Tumor imaging to confirm PR or CR should be performed at least 4 weeks after the first indication of a response is observed. Participants will then return to regular scheduled imaging every 6 weeks, starting with the next scheduled imaging time point. Participants who receive additional imaging for confirmation do not need to undergo the next scheduled tumor imaging if it is less than 4 weeks later; tumor imaging may resume at the subsequent scheduled imaging time point.

PROTOCOL NUMBER: OSU-19132

Per iRECIST (Appendix 2), disease progression should be confirmed by the site 4 to 8 weeks after first radiologic evidence of PD in clinically stable participants as defined by Appendix 2 (Note- if patient is receiving clinical benefit, oligoprogressive CNS disease that can be controlled with local therapy such as stereotactic radiation, may continue on treatment beyond progression with PI approval. Ramucirumab should be held for 2 weeks prior to radiation. Patient can have radiation for CNS oligoprogression as long as ramucirumab is held for 4-6 weeks afterwards. Ramucirumab can be restarted after this time if the patient is asymptomatic, clinically stable and this is considered appropriate by the investigator.). Participants who have unconfirmed disease progression may continue on treatment at the discretion of the Investigator until progression is confirmed by the site provided they have met the conditions detailed in Section 9.2.1.6. Participants who receive confirmatory imaging do not need to undergo the next scheduled tumor imaging if it is less than 4 weeks later; tumor imaging may resume at the subsequent scheduled imaging time point, if clinically stable. Participants who have confirmed disease progression by iRECIST, as assessed by the site, will discontinue study treatment.

6.3.6 End of Treatment and Follow-up Tumor Imaging

Patients who discontinue therapy for any reason must have an end of treatment (EOT) visit completed 30 days (\pm 14 days) after the last application of study drug.

At the EOT visit, the patients will undergo the following assessments:

Physical examination and vital signs	
• Body weight• Blood pressure, pulse, temperature• Physical examination
Urine analysis	Urine bilirubin, glucose, hemoglobin, ketones, pH, protein
Hematology	Hemoglobin, hematocrit, mean corpuscular volume, mean corpuscular hemoglobin, mean corpuscular hemoglobin concentration, white blood cell (WBC) count, WBC differential, red blood cell count, lymphocytes, monocytes, neutrophils, band neutrophils, eosinophils, basophils, platelets. WBC differential may be automated or manual as per institutional standards.
Complete serum chemistry	Sodium, potassium, chloride, bicarbonate, BUN, creatinine, glucose, calcium, phosphate, magnesium, ALT, AST, alkaline phosphatase, total bilirubin, total protein, albumin
Assessment of disease status	CT scan (if not performed within the last 28 days)
Adverse events and concomitant medication	Assessed on an ongoing basis

PROTOCOL NUMBER: OSU-19132

In participants who discontinue study treatment, tumor imaging should be performed at the time of treatment discontinuation (± 4 week window). If previous imaging was obtained within 4 weeks prior to the date of discontinuation, then imaging at treatment discontinuation is not mandatory. In participants who discontinue study treatment due to documented disease progression and the Investigator elects not to implement iRECIST, this is the final required tumor imaging.

In participants who discontinue study treatment without documented disease progression, every effort should be made to continue monitoring their disease status by tumor imaging using the same imaging schedule used while on treatment (every 12 weeks in Year 1 or every 24 weeks after Year 1) to monitor disease status until the start of a new anticancer treatment, disease progression, pregnancy, death, withdrawal of consent, or the end of the study, whichever occurs first.

6.3.7 Post-treatment follow-up

Patient status will continue to be evaluated post-study. Patients will be contacted via telephone every 3 months for the first year after study completion. Beyond 1 year post-treatment, patients will be contacted every 6 months to obtain information for post-study survival data. Patients will be asked to supply the name and addresses of two contact people who the site may contact to assist with phone follow-up. Post-study survival data may alternatively be obtained during patient visits to site or source documents from other medical visits.

6.4 End of Study

The primary statistical analysis will be performed when 80% of the events for the secondary analysis of PFS have occurred. This will ensure appropriate follow-up time for the primary endpoint of ORR and for the secondary endpoints of PFS and OS.

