1.5.2 Rationale for Starting Dose and Dosing Schedule

A phase I study evaluated ramucirumab (R) plus pembrolizumab (P) in patients with multiple tumor types, including a NSCLC cohort (n=27). One dosing regimen was evaluated in a phase 1a for NSCLC: R 10 mg/kg and P 200 mg on day 1 of 21 day cycle. The primary objective of the study was to assess safety and tolerability of R+P. The study concluded that there were no new concerning safety signals; it also demonstrated encouraging antitumor activity in previously treated NSCLC - RR 30%, median PFS 9.7 months.[45]

Based on this phase 1 data, our study will use the same dose and dosing schedule.

IRB Protocol Number: 2019C0145
IRB Approval date: 06/10/2022
Version: 05/06/2022

PROTOCOL NUMBER: OSU-19132

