3.2 Study Duration

Patients will receive pembrolizumab and ramucirumab day 1 during each 21-day cycle. Patient may continue on study drugs until disease progression or for up to 35 cycles. Objective assessment of disease progression will be performed every six weeks.

IRB Protocol Number: 2019C0145
IRB Approval date: 06/10/2022
Version: 05/06/2022

PROTOCOL NUMBER: OSU-19132

[figure not shown]
The study enrolled first patient in Summer 2020 with respect to first patient in (FPI). With an expected accrual rate of 1 patients every 2months, and a total number of 34 patients planned (if trial proceeds to second stage), the anticipated enrollment period is 60 months with the last patient enrolled by Summer2025. The anticipated length of treatment period will be approximately 3-6 months, leading to the last patient off study treatment in November-December 2025. The primary endpoint analysis will be done after the last accrued patient has been followed for at least 6 weeks.

IRB Protocol Number: 2019C0145
IRB Approval date: 06/10/2022
Version: 05/06/2022

PROTOCOL NUMBER: OSU-19132

[figure not shown]

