9.4 Analysis Plan

9.4.1 Primary endpoint analysis:

The primary study objective is to assess the overall response rate (ORR) of ramucirumab plus pembrolizumab. To do so, we will use Simon's two-stage design.²⁰ This design is implemented by first enrolling a small group of patients and then enrolling a second group of patients in the second stage conditional on an adequate number of responses in the first group. Response rate with single agent IO is around 10% and we would consider a response rate of at least 25% to be interesting for further study. The optimal two-stage design to test the null hypothesis that $P \leq 0.10$ versus the alternative that $P \geq 0.25$ will include 13 patients in the first stage. After testing the drug on 13 patients in the first stage, the trial will be terminated if 1 or fewer respond. If the trial goes on to the second stage, an additional 21 patients will be included for a total of 34 patients studied. If the

total number responding is less than or equal to 5, the drug is rejected. This design has an expected sample size of 20.95 and a probability of early termination of 0.621. The sample size was calculated using PASS 16 and assuming $\alpha = 0.10$ with a desired power of 80%.

Overall survival and progression-free survival as continuous time-to-event outcomes: All evaluable patients will be used for this analysis. Kaplan-Meier curves will be used to estimate overall survival, measured from the date of study registration to the date of event (i.e., death) or the date of last follow-up if no event has occurred at their last evaluation. We will further consider Cox proportional hazards models to explore a limited set of confounding factors.

9.4.2 Analysis of secondary endpoints:

Secondary objectives involve evaluating safety and tolerability and estimating PFS and overall survival. Descriptive statistics will be calculated for these outcomes and Kaplan-Meier curves will be calculated to estimate PFS and OS. Patients who have reached the end of the study but not progressed will be considered censored at the last documented date of contact. Estimates from this analysis will be used as preliminary data to inform future research.

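### Sections 6.4 and 3.2 time the primary analysis by different rules, and the 80%-of-PFS-events rule in 6.4 cannot ensure the follow-up it promises

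*Combined protocol and SAP*

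**What the plan says.** Section 6.4 (End of Study) sets the timing by events: "The primary statistical analysis will be performed when 80% of the events for the secondary analysis of PFS have occurred". It then claims: "This will ensure appropriate follow-up time for the primary endpoint of ORR and for the secondary endpoints of PFS and OS". It does not say what number the 80% is taken of. No planned PFS event count appears anywhere in the protocol.

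Section 3.2 (Study Duration) sets the timing by patients: "The primary endpoint analysis will be done after the last accrued patient has been followed for at least 6 weeks". Neither section refers to the other, and neither says that the later of the two applies.

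The figures that bear on the timing are:

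- Accrual (3.2): "With an expected accrual rate of 1 patients every 2months, and a total number of 34 patients planned", with "the anticipated enrollment period is 60 months with the last patient enrolled by Summer2025".
- Time on treatment (3.2): "The anticipated length of treatment period will be approximately 3-6 months".
- The only median PFS given for this combination (1.5.2, phase 1 NSCLC cohort): "RR 30%, median PFS 9.7 months".
- The final decision rule at 34 patients (9.4.1): "total number responding is less than or equal to 5, the drug is rejected".
- Response confirmation (6.3.5): first scan at 6 weeks, with confirmatory imaging at least 4 weeks after a response is first seen.

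**The concern.** A fraction of PFS events is a poor clock for a response-rate decision when accrual is slow and progression is quick. By the time the last patients enter, nearly all earlier patients have already progressed, so a high event fraction can be reached while the last patients are newly enrolled or not yet enrolled. Nothing in the 6.4 rule prevents this, yet the section presents the rule as a guarantee of follow-up.

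Two things are at stake. First, there are two rules for one analysis, and they can give different dates, so the data cut-off for the primary result is open to choice. Second, the cutoff of 5 responders is calibrated to 34 patients. Applied to fewer assessable patients, it has less power than planned, and if the cutoff were changed at that point, the stated alpha would no longer apply.

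**Working it through.** **1. The plan's own design figures.** Take p0 = 0.10, p1 = 0.25, stage 1 stop at 1 or fewer of 13, and final rejection at 5 or fewer of 34 (9.4.1).

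- Probability of early termination = P(Bin(13, 0.10) ≤ 1) = 0.621.
- Expected sample size = 13 + 21 × (1 − 0.621) = 20.95.
- Exact alpha is 0.096 and power is 0.811.

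The printed 0.621 and 20.95 reproduce. They match only the stop at 1 or fewer; the zero-response stop in the synopsis and 9.3 is a separate inconsistency and is not used here.

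**2. Inputs for the event rule.**

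- Entry every 2 months puts patient 34 at month 33 × 2 = 66. The printed 60 months does not follow from the printed rate.
- Denominator (assumed, since 6.4 gives none): 80% of 34 = 27.2, so the 28th event.
- PFS (assumed exponential): medians of 3, 4.5 and 6 months, inferred from the anticipated 3-6 months on treatment, and 9.7 months from phase 1.
- Loss: none in the base case; 10% of patients never yielding an event as a variant (assumed).

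**3. Analytic check.** Expected events at the 34th entry = Σ (1 − 2^(−2k/m)) for k = 0 to 33, where m is the median PFS.

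| Median PFS m (months) | Expected events at 34th entry | Against 28 |
|---|---|---|
| 3 | 31.3 | above |
| 4.5 | 30.2 | above |
| 6 | 29.2 | above |
| 8 | 27.7 | just below |
| 9.7 | 26.5 | below |

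The break-even median is about 8 months.

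**4. Simulation of the 28th event (40,000 trials per case).**

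| Median PFS (months) | Mean trigger month, no loss | Before 34th entry, no loss | Patients with ≥6 weeks' follow-up, no loss | Before 34th entry, 10% loss |
|---|---|---|---|---|
| 3 | 58 | 100% | 29 | 66% |
| 4.5 | 60.5 | 98% | 30 | 46% |
| 6 | 63 | 87% | 31 | 28% |
| 9.7 | 68 | 31% | 33 | 5% |

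With 10% loss, 28 events cannot occur if 7 or more of the 34 patients never yield one: P(Bin(34, 0.10) ≥ 7) = 0.048. In about 5% of trials the 6.4 date would never arrive.

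If the 34 patients enter evenly over the printed 60 months, the no-loss probabilities at 3, 4.5 and 6 months are 100%, 96% and 79%.

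**5. Operating characteristics if the cutoff of 5 were applied to fewer patients** (exact, same stage 1 rule).

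| n | Alpha | Power |
|---|---|---|
| 29 | 0.057 | 0.726 |
| 30 | 0.064 | 0.748 |
| 31 | 0.071 | 0.767 |
| 34 | 0.096 | 0.811 |

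**6. The 3.2 window.** A response first seen at the 6-week scan and confirmed at least 4 weeks later needs 6 + 4 = 10 weeks, before scan windows of ±7 days. Six weeks for the last patient is therefore too short for a confirmed response.

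**The case against.** A reader might infer that the trial is on course to be analysed at about 30 patients with reduced power. The documents do not support that. Section 3.2 already holds the primary endpoint analysis until the last accrued patient has 6 weeks of follow-up. Sections 9.2 to 9.4.1 fix the two-stage total at 34 and tie the cutoff to it. Section 6.4 neither stops accrual nor excludes later patients. The smaller analysis arises only if 6.4 is allowed to override those sections.

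The early-trigger projection is also conditional:

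- The 3-6 months is anticipated treatment length, not median PFS. Treatment can end for toxicity or continue past a first progression.
- At the one cited PFS median, 9.7 months, the trigger more often falls after full enrolment. That figure is not decisive, because Section 1.3.1 describes the phase 1 NSCLC patients as EGFR wild type.
- Modest loss to PFS follow-up lowers the probabilities sharply, and 9.4.2 does censor patients without progression.
- Section 3.1.4 contemplates additional sites after stage 1. If stage 2 accrual doubled (assumed), the no-loss probabilities would be 87%, 43% and 12% at medians of 3, 4.5 and 6 months.

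All of this limits the size of the problem. It does not remove the conflict between 3.2 and 6.4 or supply the missing denominator. Nor does it make the 6.4 rule a guarantee: even at 9.7 months without loss, the last patient would be not yet enrolled or have under 6 weeks of follow-up in about 46% of trials.

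**Conclusion.** Section 6.4 is wrong as written and should be changed. Three defects need no modelling: it conflicts with 3.2, its event fraction has no denominator, and it is tied neither to completed accrual nor to minimum follow-up, so its follow-up claim is unsupported.

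How early the rule would be met depends on assumptions. Read as 28 of 34 with no loss and a median PFS of 3-6 months, it is met before the 34th entry in 87-100% of trials, with about 29-31 patients followed for 6 weeks. With 10% never yielding an event, the range is 28-66%. At a 9.7-month median without loss it is about 31%.

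The loss of power, from 81% to about 73-77%, is what would happen if 6.4 displaced both 3.2 and the fixed sample size. It is not a projected property of the plan as a whole.

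**What to change.** - In 6.4, delete the event trigger for the primary analysis and the sentence claiming that it secures follow-up.
- In both 3.2 and 6.4, state one ORR timing: all 34 patients enrolled (13 if the trial stops at stage 1), and the last one followed long enough for a response to be confirmed under 6.3.5. That is at least about 10 weeks plus scan windows, in place of 6 weeks.
- Give PFS and OS their own cut-off, set as a minimum follow-up from the last enrolment. If an event count is kept, state its denominator, use the later of the count and the minimum follow-up, and add a fallback date in case the count is never reached.
- While editing 3.2, reconcile the 60-month enrolment period with the stated accrual rate.

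The cost is a few sentences in an amendment, with no added patients. The analyses may fall some weeks or months later than under the present wording.

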6.5 Planned Treatment of the Patients after End of Treatment Phase

After completion of the study at routine follow-up (EOT), patients will generally be treated at the discretion of the investigator according to medical routine.

6.6 Removal of Patients from Treatment

Subjects will be free to discontinue treatment or withdraw from the study at any time, for any reason, or they may be withdrawn/ removed if necessary in order to protect their health (see reasons for withdrawal below). It is understood by all concerned that an excessive rate of withdrawals can render the study uninterpretable; therefore, unnecessary withdrawal of subjects should be avoided.

If there is a medical reason for withdrawal of treatment, the patient will remain under the supervision of the investigator until the AEs have been resolved or declined to baseline values.

If a patient has failed to attend scheduled assessments in the study, the investigator must determine the reasons and circumstances as completely and accurately as possible.

In case of premature discontinuation of the study treatment, the investigations scheduled for the EOT should be performed, if possible. The CRF section entitled “End of Treatment” must be completed in all cases. Should a patient decide to withdraw, every effort will be made to complete and report the observations as thoroughly as possible. The investigator should contact

PROTOCOL NUMBER: OSU-19132

the patient to determine as completely as possible the reason for the withdrawal. A complete final evaluation at the time of the patient's withdrawal should be made, with an explanation of why the patient is withdrawing from the study. If the reason for removal of a patient from the study is an adverse event or an abnormal laboratory test result, the principal specific event or test will be recorded on the case report form.

6.7 Study Discontinuation

Early trial termination will be the result of the criteria specified below:

1. Quality or quantity of data recording is inaccurate or incomplete
2. Poor adherence to protocol and regulatory requirements
3. Incidence or severity of adverse drug reaction in this or other studies indicates a potential health hazard to participants
4. Plans to modify or discontinue the development of the study drug

In the event of decision by drug sponsor (Merck or Lilly) to no longer supply study drug, ample notification will be provided so that appropriate adjustments to participant treatment can be made.

7. TOXICITIES, RISKS AND AE-RELATED DOSE MODIFICATIONS

7.1 Ramucirumab Toxicity Overview

Ramucirumab is currently approved by the Food and Drug Administration (FDA) for commercial use in combination with docetaxel in non-small cell lung cancer. The combination of pembrolizumab with ramucirumab is investigational. The entire safety profile of the combination therapy is not known at this time. Measures will be taken to ensure the safety of the patients participating in this trial, including the use of stringent inclusion and exclusion criteria and close monitoring. Toxicity grading will be performed in accordance with NCI CTCAE version 5.0. If more than one different type of toxicity occurs concurrently, the most severe grade will determine the modification.

